## 16.2 Pharmacodynamic Summaries

### 16.2.1 IL-17 Inhibition in Whole Blood

Individual data of IL-17 concentration in stimulated and unstimulated whole blood will be listed. Descriptive statistics (n, mean, SD, geometric mean, %CV, median, min, and max) of the IL-17 whole blood concentration will be summarize by treatment and time point. Levels of BLQ will be set to 0.

Percentage of IL-17 inhibition is calculated as:

$$\frac{[(\text{stimulated concentration at baseline} - \text{unstimulated concentration at baseline}) - (\text{stimulated concentration at Rx time point} - \text{unstimulated concentration at Rx time point})]}{(\text{stimulated concentration at baseline} - \text{unstimulated concentration at baseline})} * 100\%$$

Baseline is defined as the average concentration of pre-dose (T=-18.00 hr and T=0.00 hr). Percentage of IL-17 inhibition will be listed and summarized by treatment and time point. Linear plots of the arithmetic mean of percentage of IL-17 inhibition + SD in the whole blood by scheduled sampling times will be provided for SAD part. Linear plots of the combined individual percentage of IL-17 inhibition in the whole blood by scheduled sampling times will be provided by dose of BMS-986251 and placebo.

Mean plots of percentage of IL-17 inhibition versus mean BMS-986251 plasma concentration will be provided by treatment.

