9.2 Populations for Analyses

The following populations are defined for each part of the study and will be used for analysis purposes:

Population	Description
Enrolled	All subjects who sign informed consent.
Randomized	All subjects who are randomized to a treatment, analyzed as per randomized treatment.
Safety	All subjects who had received at least one dose of BMS-986251 or placebo.
Pharmacokinetic (PK)	All subjects who receive at least 1 dose of BMS-986251 and have any available concentration-time data. Additionally, the evaluable PK population is defined as subjects who have adequate PK profiles.

Population	Description
Pharmacodynamic (PD)	All subjects who receive at least 1 dose of BMS-986251 or placebo and have any available concentration-time data for the PD assessments. Additionally, the evaluable PD population is defined as subjects who have adequate PD profiles.
Efficacy	All subjects who receive at least 1 dose of BMS-986251 or placebo and have available data for the efficacy assessments at baseline and the last visit at a minimum.

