### 3.0 Introduction

This Statistical Analysis Plan (SAP) describes the statistical methods that will be used during the analysis and reporting of data collected under Bristol-Myers Squibb Research and Development (BMS) Protocol IM024 005.

This SAP should be read in conjunction with the study protocol and electronic case report form (eCRF). This version of the plan has been developed using the final protocol version 1.0 dated 21-Sep-2017 (including all amendments up to this protocol date) and the final eCRF(s) dated 12-Feb-2018 (single ascending dose [SAD]) and 01-Jun-2018 (multiple ascending dose [MAD]).

An approved and signed SAP is a requirement for database lock. An approved SAP is also required for unblinding of the study treatments.

This SAP only covers the results that will be processed by the PRA Early Development Services (EDS) Biostatistics Department.

PRA EDS will perform the pharmacokinetic (PK), pharmacodynamic (PD), and safety and tolerability evaluation.

This SAP was written after the clinical study was terminated due to non-clinical findings. The study was stopped after completion of Part A, Cohorts A1 – A4 and during dosing of the cohort A5 and the first cohort of Part B, B1. Cohort A6 and bioavailability (BA) / food effect (FE) cohort in Part A, cohorts B2-B4 in Part B and Part C were not conducted. In this SAP, only analyses applicable for the data collected are included.

This SAP supersedes the statistical considerations identified in the protocol; where considerations are substantially different, they will be so identified. Any post-hoc or unplanned analyses, or significant changes from the planned analysis in this SAP, will be clearly identified in Section 9.8.2 of the clinical study report (CSR). Changes to planned analyses do not require an updated SAP but will be included in the CSR if significant.

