### 9.4 Pharmacodynamic

All subjects who receive at least 1 dose of BMS-986251 or placebo and have any available data for the PD assessments.

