#### 16.1.2 IL-17 Inhibition PD Parameters

**Table 6** IL-17 PD Parameters (in whole blood)

Parameter	Description	SAS Programming Notes
Imax	Maximum observed inhibition	In SAS
tImax	Time of maximum observed inhibition	In SAS
tI>50%*	Time of inhibition above 50%	
tI>90%*	Time of inhibition above 90%	

\*if feasible

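### The IL-17 inhibition formula sets no condition on its denominator: a negative baseline stimulated-minus-unstimulated difference reverses the sign, and a zero difference leaves the value undefined

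*SAP*

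**What the plan says.** SAP 16.2.1 gives the formula under the words "Percentage of IL-17 inhibition is calculated as". It takes the baseline difference between stimulated and unstimulated IL-17, subtracts the same difference at the post-dose time point, and divides by the baseline difference. The divisor therefore contains "unstimulated concentration at baseline" as a subtracted term. Baseline is the average of two pre-dose values, at -18 and 0 hours. The same section states: "Levels of BLQ will be set to 0".

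SAP 9.4 defines the PD set as "All subjects who receive at least 1 dose of BMS-986251 or placebo and have any available data for the PD assessments". Protocol 9.2 adds that "the evaluable PD population is defined as subjects who have adequate PD profiles", without saying what adequate means. The SAP's PD set does not carry that subset over, and SAP 3.0 states: "This SAP supersedes the statistical considerations identified in the protocol". SAP 8.4.1 plans no outlier analysis.

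The percentages feed the by-treatment summaries and mean plots (16.2.1), the PD parameters in Table 6 and their summaries (16.2.2), and the PK/PD scatter plot (16.2.3). Imax is described as "Maximum observed inhibition", with no upper limit.

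**The concern.** The formula measures inhibition only when stimulation raised IL-17 at baseline. If the averaged stimulated value is not above the averaged unstimulated value, there is no response to inhibit and the subject carries no information on the endpoint. The SAP still directs that a percentage be computed. With a negative divisor, a rise in IL-17 counts as inhibition and a fall counts as stimulation.

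Percentage inhibition and its derived parameters are the SAP's secondary PD endpoint (5.2.1). Each completed Part A dose level planned six active subjects, and cohort A5 dosed only four subjects in total (SAP 7.1), so one misplaced value carries much weight. It can fall on drug, where it exaggerates the effect, or on placebo, where it hides one. With no rule in the plan, someone must decide whether to keep, drop or cap the value after seeing it.

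**Working it through.** The plan states no figure to reproduce here; the check is of the formula itself.

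**Notation.** Let D be baseline stimulated minus unstimulated, and E the same difference post-dose. The SAP formula is I = 100 × (D − E) / D. When D < 0 it equals 100 × (E − D) / |D|, so any rise in the difference scores as positive inhibition. It reaches 200% once the rise is twice |D|.

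**Illustrative records** (stimulated, unstimulated; concentrations assumed, since the documents give none):

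| Baseline | Post-dose | D | E | I |
|---|---|---|---|---|
| 200, 5 | 100, 5 | 195 | 95 | 51.3% |
| 20, 25 | 60, 20 | −5 | 40 | 900% |
| 0 (BLQ), 5 | 40, 5 | −5 | 35 | 800% |
| 8, 10 | 9, 10 | −2 | −1 | 50% |
| 8, 10 | 6, 10 | −2 | −4 | −100% |
| 22, 20 | 30, 20 | 2 | 10 | −400% |
| 0 (BLQ), 0 (BLQ) | 6, 0 | 0 | 6 | undefined |

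The first row behaves as intended. Rows two to five show the sign reversed in both directions. Row six keeps the correct sign but is extreme because D is small.

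**Effect of BLQ = 0.** If both unstimulated pre-dose values are BLQ, D equals the stimulated mean and cannot be negative; it is zero if the stimulated values are BLQ too. If the stimulated values are BLQ and an unstimulated one is not, D is negative. The reversal therefore needs quantifiable unstimulated IL-17 that exceeds stimulated IL-17 after averaging.

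**Effect on a group of six.** Assume five subjects at 40% and one at 900%. Mean = (5 × 40 + 900) / 6 = 183.3%. SD = √[(5 × 143.3² + 716.7²) / 5] ≈ 351. The maximum is 900% and the median stays at 40%.

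**Frequency, under assumptions only.** Assume 30% CV per sample, two baseline samples, and a lognormal stimulated-to-unstimulated ratio with log-SD 0.7 to 1.0, floored at 1. Simulated P(D ≤ 0) per subject is p; the chance of at least one in six is 1 − (1 − p)⁶.

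| Median ratio | p | At least one in six |
|---|---|---|
| 3 | 6–10% | 31–47% |
| 5 | 1.5–4.4% | 9–24% |
| 10 | 0.1–1.0% | 1–6% |
| 20 | under 0.2% | up to 1% |

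Flooring the ratio at 1.5 instead gives p of 1.8–2.5% at ratio 3 and 0.6–1.3% at ratio 5, or 10–14% and 4–8% of six-subject groups. Under the first model, over 99% of subjects with D below zero have an Imax above 100% with no drug effect.

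**The case against.** The strongest case against is that the event may hardly occur and would be seen if it did. The SAP's own BLQ rule prevents a negative D whenever unstimulated IL-17 is unquantifiable, and nothing in the documents suggests otherwise. The frequencies above rest on assumed assay figures: at ratio 3, moving the floor from 1 to 1.5 cuts p from 6–10% to about 2%. A 900% value would stand out in the individual values of Tables 14.3.1 to 14.3.3, in Figure 14.3.5 and in the listing of stimulated and unstimulated concentrations. Imax is also summarised by its median, and the times above 50% and 90% have no mean at all. The endpoint is secondary, SAP 8.4.3 plans no formal testing, and the study had been terminated before the SAP was written.

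Most of this stands and limits the weight of the point. It does not supply the missing rule. Noticing the value is not the same as having decided in advance what to do with it, and SAP 3.0 lets analyses change without an updated SAP.

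A reader might infer that any non-responder whose IL-17 rises is scored at several hundred percent. The formula does not do that: D must be negative and the rise at least about twice |D|. A small rise gives less (50% in row four), and a small positive D gives a large negative value.

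A reader might also infer that a fixed requirement, such as stimulated at least twice unstimulated, is needed. The documents give no basis for it. Under the same assumed model, the share of true ratios below 2 at median ratio 3 is Φ[(ln 2 − ln 3)/σ], which is 28% for σ = 0.7 and 34% for σ = 1.0. At median ratio 5 it is 10–18%. Most subjects so excluded would have D above zero, where the sign is correct.

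**Conclusion.** The point holds. SAP 16.2.1 states a rule that returns a wrong-signed value when baseline D is negative and no value when D is zero, and no other section repairs it. The algebra needs no assumption. The several-hundred-percent scores and the 183% group mean are illustrations on assumed concentrations. The documents do not support any claim that this is frequent: the assumed models run from nearly half of six-subject groups to almost none. What can be said is that, with at most six active subjects per dose, a single such value would dominate the mean, SD and maximum of the secondary PD endpoint, while the median would be largely protected. The correction is worth making because it is nearly free, but it affects a descriptive secondary result and not the study's primary conclusions.

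**What to change.** Add to SAP 16.2.1 that percentage inhibition, Imax, tImax, tI>50% and tI>90% are derived only for subjects whose baseline D is above zero. Subjects with D at or below zero are flagged as not evaluable for inhibition, using pre-dose data only and before unblinding. They stay in the concentration listing and Table 14.3.1, and are counted by treatment.

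A positive-D rule does not remove extreme negative values when D is small. If the sponsor wants to limit those, it should fix an assay-based minimum response in advance and state its source.

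The cost is one sentence and one derived flag. The downside is that a rare subject with no baseline response leaves the inhibition summaries; because the flag uses only pre-dose values, treatment cannot influence who is excluded.

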### 16.2.2 Pharmacodynamic Parameters

Descriptive statistics (n, mean, SD, geometric mean, %CV, median, min, and max) will be used to summarize the calculated PD parameters by treatment. For tmax, tl>50%, and tl>90%, only n, median, min and max will be presented.

### 16.2.3 Evaluation of PK/PD correlation

PK/PD correlation will be evaluated by scatter Plot of IL-17 Inhibition versus BMS-986251 plasma concentration.

## 17.0 Safety Analyses

The safety summaries described in this section will be created using the Safety analysis set. Changes will not be provided if collections are not made during treatment periods.

### 17.1 Safety Variables

The following safety variables will be summarized:

- Treatment-Emergent Adverse Events (TEAE)
- Clinical Laboratory Evaluations
  - Clinical Chemistry
  - Hematology
  - Urinalysis
  - Coagulation
- Vital Signs
  - Systolic Blood Pressure (SBP)
  - Diastolic Blood Pressure (DBP)
  - Heart rate
  - Oral body temperature
  - Respiratory rate
- Electrocardiograms (ECG)
  - Heart Rate
  - PR Interval
  - QRS-Duration

- QT Interval
- QTc (Frederica) Interval
- T-Wave Assessment
- U-Wave Assessment
- Physical Examination
- Taste questionnaire

### 17.1.1 Adverse Events

An AE is defined as any new untoward medical occurrence or worsening of a preexisting medical condition in a clinical investigation participant that does not necessarily have a causal relationship with treatment. AE summaries will include only TEAEs. TEAEs are those which occur after the first dose of study drug. All TEAE summaries will be presented alphabetically by system organ class, with preferred terms sorted in decreasing order of frequency within each system organ class based on MedDRA version 21.0.

TEAEs occurring following dosing in a specific period but before dosing in the following period will be attributed to that specific period. If the time is missing for an AE on a dosing day then the AE will be attributed to the treatment given on that day.

The following missing data will be imputed (for calculations only) as defined:

- Missing AE start and / or end times for the calculation of onset and duration will be assumed to be at 00:01 for a start time and 23:59 for end times
- Missing AE severity or relationship will be left as missing
- Missing AE start times for the determination of treatment emergence will be assumed to occur after treatment unless partial date documents the AE as happening prior to treatment
- Missing AE start times for the determination of treatment assignment will be assumed to occur after treatment on the recorded date one minute after dosing
- Missing AE start date will be assumed to be after treatment for the determination of TEAE, but will not be attributed to a specific treatment in studies with multiple treatments.

A summary of the number and percentage of subjects reporting TEAEs, serious AEs (SAEs), who discontinue study drug due to a TEAE, and will be presented by treatment and overall.

A summary of the number and percentage of subjects reporting each TEAE will be presented by treatment and overall. Counting will be done by subject only, not by event; subjects will only be counted once within each body system or preferred term.

A summary of the number and percentage of subjects reporting each TEAE will be presented by relationship to study drug (as recorded on the eCRF) and by treatment and overall. Subjects with multiple events within a particular system organ class (SOC) or preferred term will be counted as related unless no events were related in that SOC/preferred term.

A summary of the number and percentage of subjects reporting each TEAE will be presented by severity (as recorded on eCRF) and by treatment and overall. Subjects with multiple events within a particular system organ class or preferred term will be counted under the category of their most severe event within that system organ class or preferred term.

All AEs (including non-treatment-emergent events) recorded on the eCRF will be listed by subject.

A separate listing of AEs leading to study drug discontinuation will be provided.

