8.3.5 Withdrawal and Replacement of Subjects

8.3.5.1 Discontinuation of Treatment

Subjects MUST discontinue IP or study procedures (in case of single dose treatments) for any of the following reasons:

- Subject's request to stop study treatment. Subjects who request to discontinue study treatment will remain in the study and must continue to be followed for protocol specified follow-up procedures. The only exception to this is when a subject specifically withdraws consent for any further contact with him/her or persons previously authorized by subject to provide this information.
- Any clinical AE, laboratory abnormality or intercurrent illness which, in the opinion of the Investigator, indicates that continued participation in the study is not in the best interest of the subject.
- Termination of the study or program by BMS.
- Loss of ability to freely provide consent through imprisonment or involuntarily incarceration for treatment of either a psychiatric or physical (eg, infectious disease) illness.
- Abnormal liver tests suggestive of drug-induced liver injury (DILI) as defined in Section 8.5.2.1.7.
- Inability to comply with protocol.
- Stopping rules as defined in Section 8.3.5.5 are met.
- Discretion of the Investigator.

If study treatment is discontinued prior to the subject's completion of the study, the reason for the discontinuation must be documented in the subject's medical records and entered on the appropriate electronic case report form (eCRF) page. As indicated, appropriate follow-up and/or alternate medical care must be arranged for the subject.

Refer to the Schedule of Activities (Section 1) for data to be collected at the time of treatment discontinuation and follow-up and for any further evaluations that can be completed.

All subjects who discontinue study treatment should comply with protocol specified follow-up procedures as outlined in Section 1. The only exception to this requirement is when a subject withdraws consent for all study procedures including post-treatment study follow-up or loses the ability to consent freely (ie, is imprisoned or involuntarily incarcerated for the treatment of either a psychiatric or physical illness). Replacement of subjects is described in Section 8.3.5.4.

To the greatest extent possible, subjects who discontinue study treatment will remain in the study for continued follow-up.

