8.3.5.2 Discontinuation from the Study

Subjects who request to discontinue study treatment will remain in the study and must continue to be followed for protocol specified follow-up procedures. The only exception to this is when a subject specifically withdraws consent for any further contact with him/her or persons previously authorized by subject to provide this information. Expectations are as follows:

- Subjects should notify the Investigator of the decision to withdraw consent from future follow-up in writing, whenever possible.
- The withdrawal of consent should be explained in detail in the medical records by the Investigator, as to whether the withdrawal is from further treatment with study treatment only or also from study procedures and/or post-treatment study follow-up, and entered on the appropriate eCRF page.
- In the event that vital status (whether the subject is alive or dead) is being measured, publicly available information should be used to determine vital status only as appropriately directed in accordance with local law.
- If the subject withdraws consent for disclosure of future information, the Sponsor may retain and continue to use any data collected before such a withdrawal of consent.

The following procedures must be performed upon subject withdrawal:

- Assessments for the end of treatment visit must be performed, provided that the subject has not withdrawn consent for these activities.
- All required eCRF pages must be completed, including the date of and explanation for the withdrawal.

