8.3.5.4 Replacement of Subjects

Rescreening is discussed in Section 8.3.4.

Subjects will not be replaced if they are discontinued from the study secondary to an AE unless the AE can be determined to be unrelated to treatment. Subjects who are discontinued from the study for reasons not related to an adverse or other safety observation may be replaced. The replacement subject will receive the same treatment as the subject being replaced.

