##### 5.1.1 Primary Endpoint

###### Safety and tolerability

- Number and percent of subjects that experience the following: SAE, death or an AE leading to study discontinuation, during the study participation or up to 1 month post discontinuation of dosing or last participation in the study for SAE.
- Number and percent of subjects with potentially clinically significant changes in ECG parameters, vital signs, or clinical laboratory parameters from Day 1 through the final follow visit.

Other safety measures collected during the study are not considered among the primary endpoint and will be summarized as safety endpoints.

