Table 14.4.4.2	Summary of Safety Laboratory Results	Safety
Table 14.4.4.3	Shift Summary of Laboratory Results by Reference Range and Time Point	Safety
Table 14.4.4.4	Summary of Vital Signs	Safety
Figure 14.4.4.5	Plots of mean change from baseline of Vital Signs	Safety
Table 14.4.4.6	Summary of 12-Lead Electrocardiograms	Safety

List of End of Text Listings:	
Output	Title
Section 16.2.1 – Disposition	
Listing 16.2.1.1	Subject Disposition
Listing 16.2.1.2	Tuberculosis Screening
Section 16.2.2 – Protocol Deviations	
Listing 16.2.2	Important Protocol Deviations
Section 16.2.3 – Excluded Subjects	
Listing 16.2.3	Analysis Sets
Section 16.2.4 – Demographics and Baseline Characteristics	
Listing 16.2.4.1	Subject Demographics
Listing 16.2.4.2	Medical History
Listing 16.2.4.3	Prior and Concomitant Medications
Listing 16.2.4.4	Tobacco and Alcohol Use
Section 16.2.5 - Compliance	
Listing 16.2.5.1	Study Drug Administration
Section 16.2.6 – Response Data	
Listing 16.2.6.1	Plasma BMS-986251 Concentrations
Listing 16.2.6.2	Plasma Pharmacokinetic Parameters
Listing 16.2.6.3	Urine BMS-986251 Concentrations and Amounts Excreted

Listing 16.2.6.4	Urine Pharmacokinetic Parameters
Listing 16.2.6.5	IL-17 Concentrations in Stimulated and Unstimulated Whole Blood
Listing 16.2.6.6	IL-17 Inhibition in Whole Blood
Listing 16.2.6.7	IL-17 Inhibition in Whole Blood Pharmacokinetic Parameters
Section 16.2.7 – Adverse Events Data	
Listing 16.2.7.1	Adverse Events
Listing 16.2.7.2	Adverse Events Leading to Study Drug Discontinuation
Section 16.2.8 – Laboratory Data	
Listing 16.2.8.1	Clinical Laboratory Results – Chemistry
Listing 16.2.8.2	Clinical Laboratory Results – Hematology
Listing 16.2.8.3	Clinical Laboratory Results – Urinalysis
Listing 16.2.8.4	Clinical Laboratory Results – Serology
Listing 16.2.8.5	Clinical Laboratory Results – Pregnancy
Listing 16.2.8.6	Clinical Laboratory Results – Drug and Alcohol Screen
Listing 16.2.8.7	Clinical Laboratory Results – Comments
Section 16.2.9– Other Safety Data	
Listing 16.2.9.1	Vital Signs
Listing 16.2.9.2	12-Lead Electrocardiograms
Figure 16.2.9.3	Scatter Plots of $\Delta$ QTcF Versus BMS-986251 Plasma Concentration
Listing 16.2.9.4	Physical Examinations
Listing 16.2.9.5	Taste Questionnaire

Other Appendix Outputs:	
Output	Title
Appendix 16.1.7	Randomization
Appendix 16.1.9.2	Statistical Appendices

---

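### Does wording the AE outputs on study drug discontinuation leave the primary endpoint's AEs leading to study discontinuation unreported?

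*SAP*

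**What the plan says.** The endpoint, worded alike in Protocol 9.3.1 and SAP 5.1.1, counts subjects with "SAE, death or an AE leading to study discontinuation".

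The AE outputs in the SAP use a different event. The overview in SAP 17.1.1 counts subjects "who discontinue study drug due to a TEAE". Later in the section: "A separate listing of AEs leading to study drug discontinuation will be provided". In Appendix 4, Listing 16.2.7.2 is titled "Adverse Events Leading to Study Drug Discontinuation".

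The protocol keeps the two events apart:

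- Section 8.3.5.1, on treatment: "To the greatest extent possible, subjects who discontinue study treatment will remain in the study for continued follow-up".
- Section 8.3.5.2, on leaving the study, has the investigator record "as to whether the withdrawal is from further treatment with study treatment only or also from study procedures and/or post-treatment study follow-up".
- Section 8.3.5.4, on replacement, has a rule for study discontinuation alone: "Subjects will not be replaced if they are discontinued from the study secondary to an AE", with an exception for unrelated events.

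Section 8.3.5.1 also introduces its list of reasons with a clause for single dosing: "Subjects MUST discontinue IP or study procedures (in case of single dose treatments) for any of the following reasons".

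**The concern.** A primary safety component should be reported as it is defined. Here the definition names one event and the AE summary and listing name another, and SAP 7.1 does not declare the difference as a change from the protocol.

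The mismatch also sits badly with the data in hand. Part A is single-dose, so after Day 1 there is no further drug to stop. A programmer who took the SAP wording literally could produce a row that must be zero in Part A whatever happened, and a zero of that kind says nothing about tolerability. In Part B the same row could count someone who stopped drug but stayed for follow-up, which is not the endpoint event. At stake is whether the report shows the component as defined.

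**Working it through.** The documents state no figure for this component, so there is none to reproduce. The check is a headcount and then a comparison of outputs.

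**Headcount (SAP 7.1).** Part A: 8 + 8 + 8 + 8 + 4 = 36 dosed. Part B: 2 dosed, until Day 10. Total: 36 + 2 = 38. Share in single-dose Part A: 36/38 = 94.7%. This is the share of subjects for whom the literal phrase does not fit. It is not a share misreported, which depends on how many AE-related withdrawals occurred.

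**Which planned output captures which event.** SAP 10.0 counts subjects who withdrew from the study early, as number and percentage, broken down by reason. Four cases cover the possibilities:

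| Case | Endpoint event? | Disposition by reason | Drug-discontinuation row, literal |
|---|---|---|---|
| Part A, leaves study for an AE after the dose | Yes | Counted | Missed |
| Part B, stops drug for an AE, stays in study | No | Not counted | Counted |
| Part B, stops drug and leaves study for an AE | Yes | Counted | Counted |
| Part B, leaves study for an AE after the last dose | Yes | Counted | Missed |

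The disposition column agrees with the endpoint in all four rows. The literal AE row fails in three, but it is not the only source.

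**Whether the disposition output reaches the right groups.** Appendix 4 assigns Table 14.1.2 to all analysis sets, which includes the Safety set. SAP 8.1.4 has summaries by study part and treatment. SAP 7.1 keeps a disposition summary for Part B. Listing 16.2.1.1 gives disposition by subject, and SAP 17.1.1 lists every AE by subject. Protocol 8.3.5.2 has the date of and explanation for a withdrawal entered in the eCRF, so the reason should be in the data.

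**Whether the literal reading is the right one.** Protocol 8.3.5.1, under a heading about treatment, extends discontinuation to study procedures for single doses, and an AE judged by the investigator to rule out continued participation is one of its listed reasons. On that reading the SAP phrase can capture the first row of the table.

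**Whether the AE table omits the count.** The overview sentence in SAP 17.1.1 breaks off: after the drug-discontinuation item comes a conjunction with nothing behind it. An item may have been lost there. Appendix 5 puts the shells in a separate document, so the rows of Table 14.4.1.1 cannot be read.

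**The case for a change.** The strongest reply is that a primary component should not have to be assembled. SAP 10.0 does not name AE as a reason category, does not tie the disposition table to the endpoint, and does not identify which AE was responsible. Its percentages are on the analysis-set total, while SAP 8.1.3 uses treatment-group denominators. The broken sentence needs repair in any case, and the wording for the listing is intact and consistent in both places. A reassuring zero also has value only if the row could have recorded something else.

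Much of this stands as a comment on presentation. It does not show that the component goes unreported. The endpoint is a number and percent, and disposition supplies both. The listing is a supporting output, and Protocol 9.4.2.1 promises only a listing of AEs leading to discontinuation, without saying of what. If treatment-group percentages are wanted, the withdrawal counts and group sizes are all available. The point about an uninformative zero applies to the AE row read literally, not to the disposition table, which can record withdrawals in both parts.

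For Part B, SAP 3.0 attributes the stop to non-clinical findings while B1 was being dosed and mentions no AE-related stop. Nothing in the documents supports an actual miscount among the two subjects.

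**Conclusion.** The wording differs and the protocol does distinguish the two events, but no change to the plan is called for. Followed as written, the plan still yields study withdrawals by reason, by part and treatment, with subject-level AE detail beside them. Changing the AE row and the listing title would relabel or move information that is already planned. A statistician preparing the report would take the component from Table 14.1.2 and check it against Listing 16.2.1.1 and the AE listing.

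No effect on any result is shown. The documents report no AE-related discontinuation in either part, and SAP 8.4.3 plans no formal test. The figure of 36 of 38 describes who was in single-dose Part A, not an error rate.

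This rests on two assumptions that the documents support but do not prove: that AE is among the withdrawal reasons collected, and that disposition records leaving the study, as SAP 10.0 is worded, and not merely stopping drug. If the shells or the eCRF contradicted either one, the count would have to be rebuilt from the subject-level listings, which remains feasible with 38 dosed subjects.
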